#### Radiographic Progression-Free Survival (rPFS) by IRC

rPFS is defined as the time from the date of the first dose of study drug to radiographic disease progression or death due to any cause, whichever occurs first. Censoring rules for rPFS will be described in Appendix 10.2. For this secondary efficacy endpoint, the tumor assessments will be performed by the IRC and will be summarized for the Safety Analysis Set (Cohorts 1 and 2).

rPFS will be estimated using the Kaplan-Meier method, and the median rPFS will be presented along with its 2-sided 95% confidence interval using the Brookmeyer and Crowley method. The event-free rate at select timepoints will be calculated along with 2-sided 95% confidence

intervals using Greenwood's formula. The median follow-up will be estimated using the reverse Kaplan-Meier.

### Overall Survival (OS)

OS is defined as the time from the date of the first dose of study drug to death due to any cause. Patients who remained alive before data cutoff or discontinuation of the study (discontinued study due to reasons other than "Death") will be censored at the time of data cutoff or the last date the patient was known to be alive. This secondary efficacy endpoint will be summarized for the Safety Analysis Set (Cohorts 1 and 2).

OS will be estimated using the Kaplan-Meier method, and the median OS will be presented along with its 2-sided 95% confidence interval using the Brookmeyer and Crowley method. The event-free rate at select timepoints will be calculated along with 2-sided 95% confidence intervals using Greenwood's formula. The median follow-up will be estimated using the reverse Kaplan-Meier.

[figure not shown]
[figure not shown]
[figure not shown]
### **6.4.3 Subgroup Analyses**

The primary efficacy endpoints of ORR and PSA response rate will be summarized within their respective analysis populations for the following subgroups:

- Age group (< 65 years vs  $\geq$  65 years)
- Race (White vs other)
- Geographic Region (North America vs rest of world)
- ECOG performance status (0 vs 1)
- BRCA 1/2-mutant status (mutated vs unmutated)
- Number of prior lines of therapy (0-2 vs 3+)

### **6.4.4 Exploratory Efficacy Endpoints**

**Table 3 Exploratory Efficacy Endpoint Analysis Populations**

## 6.5 SAFETY ANALYSES

All safety analyses will be performed by cohort and overall for the Safety Analysis Set. The incidence of treatment-emergent adverse events (TEAEs) will be summarized. Laboratory test results and vital signs will be provided in listings.

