Time-to-event variables of DOR, duration of PSA response, time to PSA progression, time to SSE, rPFS, and OS will be estimated using the Kaplan-Meier method. Median of these time-to-event variables will be presented along with their 2-sided 95% CI using the Brookmeyer and Crowley method.

Descriptive statistics will be provided for time to objective response and time to PSA response. Only responders will be included in analyses for DOR, duration of PSA response, time to response, and time to PSA response.

The ORR as assessed by investigator and its exact 2-sided 95% CI will be reported.

Pharmacokinetic Analyses:

Pamiparib concentrations will be summarized by nominal time of collection. Descriptive statistics will include means, medians, ranges, and standard deviations, as appropriate.

Population PK analysis may be carried out to include plasma concentrations from this study in an existing model. Additional PK parameters such as apparent clearance (CL/F) of the drug from plasma and area under the plasma concentration-time curve from 0 to 12 hours postdose (AUC_{0-12}) may be derived from the population PK analysis if supported by data.

Exposure-response (efficacy or safety endpoints) analysis may be carried out if supported by data. The results of the population PK and exposure-response analyses may be reported separately from the clinical study report.

Exploratory Efficacy Analyses:

[REDACTED]

[REDACTED]
[REDACTED]
[REDACTED]

Safety Analysis:

All TEAEs including, serious AEs, deaths, \geq Grade 3 TEAEs, pamiparib-related TEAEs, and TEAEs that led to pamiparib withholding or permanent discontinuation, will be summarized. Pamiparib exposure, vital sign measurements, electrocardiogram findings, and clinical laboratory results will also be summarized.

Sample Size:

This study is designed to provide adequate power for primary endpoints of ORR and PSA response rate. A sample size of approximately 100 patients is planned (at approximately 45 centers with a projected average enrollment of 2 to 3 patients per center).

Assuming ORR of 35% for pamiparib in CTC-HRD-positive patients versus 15% for historical control in patients with measurable disease, the study power is 88% using a binomial exact test and 1-sided type-I error of 0.025 with $n = 50$. The binomial exact 95% CI of 35% ORR is 22.1% to 49.8% with a sample size of 50 patients.

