10.5.2. Adverse Events

The AE will be coded using Medical Dictionary for Regulatory Activities Version 20.0 or higher and graded using NCI-CTCAE Version 4.03 or higher.

A TEAE is defined as an AE that had an onset date on or after first dose of pamiparib or was worsening in severity from baseline (pretreatment) up to 30 days following permanent discontinuation of pamiparib or initiation of new anticancer therapy, whichever occurs first. All TEAEs will be included in summary tables and in-patient data listings.

The incidence of TEAEs will be reported as the number (percentage) of patients with TEAEs by system organ class and preferred term. A patient will be counted only once by the highest grade according to NCI-CTCAE Version 4.03 or higher within a system organ class and preferred term, even if the patient experienced more than one TEAE within a specific system organ class and preferred term. The number (percentage) of patients with TEAEs will also be summarized by relationship to the study treatment. Treatment-related AEs include those events considered by the investigator to be related to study treatment or with missing assessment of the causal relationship. SAEs, deaths, TEAEs \geq Grade 3, pamiparib-related TEAEs, and TEAEs that led to pamiparib withholding or permanent discontinuation will also be summarized.

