10.5.4. Physical Examinations

Physical examination results collected in association with an AE will be listed and summarized.

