10.5.5. Vital Signs

Specific vital signs (eg, blood pressure and temperature) will be summarized and listed. The change from baseline will also be presented.

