10.5.6. Electrocardiograms

The percentage of patients with abnormal and clinically significant ECG findings will be presented.

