### 6.5.2 Adverse Events

AEs will be graded by the investigators using CTCAE v4.03. The AE verbatim descriptions (investigator terms from the CRF) will be classified into standardized medical terminology using the Medical Dictionary for Regulatory Activities (MedDRA) Version 20.0 or higher.

A treatment emergent adverse event (TEAE) is defined as an AE that had an onset (including worsening from pretreatment) date on or after the first dose of study treatment through 30 days after the last dose of study treatment or initiation of new anti-cancer therapy, whichever occurs first. Only TEAEs will be included in summary tables. All AEs, treatment emergent or otherwise, will be presented in patient data listings.

An overview table, including the number and percentage of patients with TEAEs, serious TEAEs, grade 3 or higher TEAEs, treatment-related TEAEs, TEAEs that led to death, and TEAEs that led to treatment discontinuation, dose reduction or dose interruption will be provided. Treatment-related TEAEs include those events considered by the investigator to be related to study treatment or with missing assessment of the causal relationship.

The incidence of TEAEs will be reported as the number and percentage of patients with TEAEs by SOC and PT. A patient will be counted only once by the highest severity grade within an SOC and PT, even if the patient experienced more than 1 TEAE within a specific SOC and PT. The number and percentage of patients will be summarized by SOC and/or PT for the following:

- TEAEs

- Treatment Related Grade 3 or higher TEAEs
- Serious TEAEs
- TEAEs that led to treatment discontinuation
- TEAEs that led to dose modification

TEAEs will also be summarized by PT in descending order. A listing of all AEs and AEs that led to treatment discontinuation will be provided.

All deaths and causes of death will be provided in a listing, including those occurring during the study treatment period and those reported during the survival follow-up period after treatment completion/discontinuation.

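### SAP 6.5 specifies no ECG output and reduces vital signs to listings, contrary to Protocol 10.5, while SAP 8 presents the safety analyses as unchanged

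*SAP*

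**What the plan says.** Protocol 10.5 names laboratory values, vital signs, physical examinations and ECGs as evidence on safety alongside adverse events, and then gives each its own output.

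- ECG (Protocol 10.5.6): "The percentage of patients with abnormal and clinically significant ECG findings will be presented".
- Vital signs (Protocol 10.5.5): "Specific vital signs (eg, blood pressure and temperature) will be summarized and listed", followed by "The change from baseline will also be presented".
- Physical examination (Protocol 10.5.4): "Physical examination results collected in association with an AE will be listed and summarized".
- The protocol synopsis repeats the main commitment: "vital sign measurements, electrocardiogram findings, and clinical laboratory results will also be summarized".

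SAP 6.5 opens with one sentence on these data: "Laboratory test results and vital signs will be provided in listings". Its four subsections cover exposure, adverse events, laboratory values and ECOG performance status. In the SAP text ECG appears only as an entry in the abbreviation list.

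SAP 8 records the consequences of stopping after 13 patients. It says in general terms that the report will not contain every analysis in the protocol. It then says exposure, safety and PK analyses proceed as planned, and that the ECOG shift table is dropped.

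**The concern.** The final report will contain no efficacy tables (SAP 8), so safety is most of what it can offer. A reader told that safety was analysed as planned would expect the Protocol 10.5 outputs to be there. Someone programming from SAP 6.5 would produce no ECG output of any kind and no summary of vital signs.

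ECGs are a substantial part of the safety data. Protocol 7.4.3 has PR interval, QRS duration and QTcF assessed at each recording. Appendix 1 schedules ECGs at screening, at every treatment visit and at end of treatment. Protocol Table 4 makes QTc one of its dose-modification criteria. At stake is whether data collected from every treated patient for a stated safety purpose reach the report, and whether the SAP describes its own departures from the protocol accurately.

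**Working it through.** No figure in the plan is in dispute, so the check is mainly a comparison of texts.

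**Step 1: is the gap a redaction?** No. The SAP table of contents lists 6.5.1 Extent of Exposure, 6.5.2 Adverse Events, 6.5.3 Laboratory Values and 6.5.4 ECOG Performance Status, then moves to 6.6. There is no hidden ECG, vital-sign or physical-examination subsection.

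**Step 2: promise against plan.**

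| Item | Protocol 10.5 | SAP 6.5 | Named as a change in SAP 8? |
|---|---|---|---|
| ECG | Percentage of patients with abnormal and clinically significant findings | No table, no listing | No |
| Vital signs | Summary, listing, change from baseline | Listing only | No |
| Physical examination tied to an AE | Listing and summary | Nothing | No |
| Laboratory values | By CTCAE grade, shift tables as appropriate | By grade with shift tables (6.5.3), despite the opening sentence of 6.5 | Not needed |
| ECOG shift table | Not in Protocol 10.5 | Planned (6.5.4) | Yes, dropped |

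SAP 8 goes down to the level of a single table for ECOG. Its silence on the first three rows therefore reads as a statement that they stand.

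**Step 3: where does an ECG finding go if the SAP is followed?**

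- Judged clinically significant by the investigator: Protocol 9.1.5 has it recorded as an AE or SAE. If treatment-emergent, it enters the SAP 6.5.2 tables, including those for events leading to discontinuation or dose modification.
- Abnormal but not judged clinically significant, or a measured interval not reported as an AE: it appears in no specified output.

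Vital-sign values all remain visible in listings. What is lost there is the summary and the change from baseline.

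**Step 4: scale.** Inputs: 13 patients (SAP 8); ECG visits from Appendix 1.

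- One patient: 1/13 = 7.7 percentage points.
- If no patient has a given finding, the exact two-sided 95% upper limit is 1 − 0.025^(1/13) = 1 − 0.753 = 24.7%.
- Scheduled ECGs through Cycle 2 Day 15: 1 at screening + 2 in Cycle 1 + 2 in Cycle 2 = up to 5 per patient. If all 13 patients reached that visit, that is up to 13 × 5 = 65 recordings. The documents do not say how many did, so this is a ceiling for those visits.

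**The case against.** Four points on the other side deserve weight.

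1. **Clinically significant ECG findings are not lost.** The AE route in Protocol 9.1.5 carries them into the TEAE tables, and that section counts leading to dose interruption or discontinuation as a sign of clinical significance. This stands. A reader might infer that QT events would go untabulated. The documents do not support that: a QTc event that triggered the Table 4 criteria would normally be an AE. Nor does the protocol promise a QTc analysis; it promises only a percentage with abnormal and clinically significant findings. If that phrase means findings that are both, the lost table would largely duplicate AE data, scattered across preferred terms. If it means two categories, the merely abnormal findings vanish.

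2. **Severe adverse events.** The by-term list in SAP 6.5.2 includes "Treatment Related Grade 3 or higher TEAEs", and a reader might infer that all-cause severe events have been dropped. They have not. Protocol 10.5.2 says of events at or above "Grade 3, pamiparib-related TEAEs, and TEAEs that led to pamiparib withholding or permanent discontinuation will also be summarized", without requiring a table by SOC and preferred term. The SAP overview table counts all-cause Grade 3 or higher TEAEs, and all TEAEs are tabulated by SOC and preferred term with each patient counted at highest grade. The contrast between all-cause and related severe events in the Phase 1 data (Protocol 1.5.2.3) therefore measures nothing that is missing here.

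3. **SAP 8 does warn that some planned analyses are omitted, and SAP 1 ties the SAP to protocol Version 1.0.** One could read the as-planned statement as covering Protocol 10.5.6. That does not resolve the conflict. If it points to the protocol, SAP 6.5 contradicts it on vital signs; if it points to SAP 6.5, there is no ECG output.

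4. **With 13 patients, listings may be enough.** That is fair for vital signs. It does not help ECGs, which have no listing either. The ECG point does rest on silence across SAP 6.5, whereas the vital-sign point rests on an explicit sentence.

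**Conclusion.** The point holds for ECG, vital signs and AE-associated physical examinations: SAP 6.5 provides less than Protocol 10.5 promises, and SAP 8 does not declare it. ECG matters most, because findings not recorded as AEs have no place in any table or listing. The vital-sign and physical-examination gaps are smaller: vital-sign values are listed, and each examination result in question is tied to an AE that is itself reported.

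It does not extend to severe adverse events, nor to a claim that QT events would be hidden. No test, estimate or error rate is affected, and at 13 patients the missing tables carry little inferential weight. The conclusion assumes that the report follows SAP 6.5 as written and that Protocol 9.1.5 was applied at the sites.

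**What to change.** In SAP 6.5:

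- Add a table of the number and percentage of patients with abnormal, and with clinically significant, ECG findings after baseline, plus an ECG listing.
- Optionally add rows counting QTcF above 500 msec and QTc change above 60 msec, the values already in Protocol Table 4. These are descriptive and go beyond the protocol's commitment. If they are used, state the reference for change: Table 4 uses the highest baseline or predose value, whereas SAP 6.2.1 defines baseline as the last value on or before first dose.
- Add a vital-sign summary by visit with change from baseline, using the continuous statistics in SAP 6.2.2.
- Add the AE-associated physical-examination output, or declare it dropped.
- Limit the opening listings sentence to what is truly listed only, since SAP 6.5.3 also summarises laboratory values.

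In SAP 8, qualify the as-planned statement by naming each Protocol 10.5 output still omitted, with the reason. An all-cause Grade 3 or higher table by SOC and preferred term would be an optional extra, not a correction.

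The cost is a few descriptive tables on 13 patients, assuming the ECG interpretation and values are in the database (the case report form is not among the documents). If the sponsor prefers no new tables, an ECG listing and an accurate SAP 8 are the least that would make the plan consistent.

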### 6.5.1 Extent of Exposure

The number (and percentage) of patients requiring dose reductions, dose missed and dose on hold will be summarized. One cycle is defined as 28 days of treatment. The duration of treatment (days) will be summarized with descriptive statistics.

Actual dose intensity per patient (in mg/day) and relative dose intensity (total dose received / total dose planned) per patient will be summarized. Actual dose intensity is calculated as the total dose (mg) taken by a patient divided by overall duration of exposure (= Date of last non-zero dose – Date of first dose + 1) for individual patient. Relative dose intensity is calculated as the total dose (mg) taken by a patient divided by the total dose planned for the patient by study design.

Patient data listings will be provided for all dosing records, including dose reduction, dose missed and treatment discontinuation.

### 6.5.2 Adverse Events

AEs will be graded by the investigators using CTCAE v4.03. The AE verbatim descriptions (investigator terms from the CRF) will be classified into standardized medical terminology using the Medical Dictionary for Regulatory Activities (MedDRA) Version 20.0 or higher.

A treatment emergent adverse event (TEAE) is defined as an AE that had an onset (including worsening from pretreatment) date on or after the first dose of study treatment through 30 days after the last dose of study treatment or initiation of new anti-cancer therapy, whichever occurs first. Only TEAEs will be included in summary tables. All AEs, treatment emergent or otherwise, will be presented in patient data listings.

An overview table, including the number and percentage of patients with TEAEs, serious TEAEs, grade 3 or higher TEAEs, treatment-related TEAEs, TEAEs that led to death, and TEAEs that led to treatment discontinuation, dose reduction or dose interruption will be provided. Treatment-related TEAEs include those events considered by the investigator to be related to study treatment or with missing assessment of the causal relationship.

The incidence of TEAEs will be reported as the number and percentage of patients with TEAEs by SOC and PT. A patient will be counted only once by the highest severity grade within an SOC and PT, even if the patient experienced more than 1 TEAE within a specific SOC and PT. The number and percentage of patients will be summarized by SOC and/or PT for the following:

- TEAEs

- Treatment Related Grade 3 or higher TEAEs
- Serious TEAEs
- TEAEs that led to treatment discontinuation
- TEAEs that led to dose modification

TEAEs will also be summarized by PT in descending order. A listing of all AEs and AEs that led to treatment discontinuation will be provided.

All deaths and causes of death will be provided in a listing, including those occurring during the study treatment period and those reported during the survival follow-up period after treatment completion/discontinuation.

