9.3. Timing, Frequency, and Method of Capturing Adverse Events and Serious Adverse Events

9.3.1. Adverse Event Reporting Period

After the ICF has been signed, but before initiation of pamiparib, only SAEs should be reported to the sponsor.

After initiation of treatment, all AEs and SAEs, regardless of relationship to treatment, will be reported until 30 days after the last dose of pamiparib or initiation of new anticancer therapy, whichever occurs first. After this period, the investigator should report any SAEs that are believed to be related to prior study drug treatment.

After a patient is discontinued from the study, investigators are not obligated to actively seek AEs or SAEs from the former patients. However, if the investigator learns of any SAE, including a death, at any time, and considers the SAE related to pamiparib, the investigator will notify the sponsor.

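### Related SAEs starting after the TEAE window, and deaths not due to a TEAE, reach only the listings; SAP 6.5.2 should add summary rows for them

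*SAP*

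**What the plan says.** **Window.** SAP 6.5.2 counts an AE as treatment-emergent if its onset, or its worsening from pretreatment, falls on or after first dose and "through 30 days after the last dose of study treatment or initiation of new anti-cancer therapy, whichever occurs first". Protocol 10.5.2 ends the period at the same point.

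**Tables and listings.** SAP 6.5.2 says: "Only TEAEs will be included in summary tables. All AEs, treatment emergent or otherwise, will be presented in patient data listings". The overview table covers, among others, "serious TEAEs, grade 3 or higher TEAEs, treatment-related TEAEs, TEAEs that led to death". The tables by system organ class and preferred term are also all TEAE-based. Deaths and their causes go into a listing that also covers "those reported during the survival follow-up period after treatment completion/discontinuation".

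**Collection after the window.** Protocol 9.3.1 states: "After this period, the investigator should report any SAEs that are believed to be related to prior study drug treatment". It gives no end date, and footnote o of the schedule of assessments (Protocol Appendix 1) says the same. Once a patient has left the study, investigators need not look for events, but they notify the sponsor of any related SAE they learn of.

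**What the protocol plans to summarise.** Protocol 10.5.2 puts all TEAEs into tables, without saying that nothing else may go there. Its list of further summaries begins "SAEs, deaths, TEAEs"; the TEAE label is attached to the later items but not to the first two. The Safety Analysis paragraph of the synopsis instead names serious AEs and deaths as components of the TEAE summary.

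**Current status.** SAP 8 reports that the trial stopped after 13 patients and that safety analyses go ahead as planned. It records no narrowing of the SAE or death summaries.

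**The concern.** Collection and tabulation have different boundaries. The protocol keeps collecting one class of event after the window, namely serious events the investigator attributes to the drug, and the SAP then keeps that class out of every AE table. The window can also close well before 30 days. As an illustration, if the next therapy starts on day 8 after last dose, a related SAE with onset on day 9 is outside it.

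Myelodysplastic syndrome and acute myeloid leukaemia are the obvious candidates. Protocol 1.8 names them as risks of PARP inhibitors, to be reported as SAEs. Protocol 6.1.4 has marrow investigation considered when blood counts have not recovered after 4 weeks of interruption. If dosing does not resume and onset is dated to the diagnosis, the event can fall beyond day 30.

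Any omission works in one direction: it can lower the tabulated related serious or fatal toxicity but cannot raise it. At stake is whether a reader who relies on the tables sees everything the trial collected on such events.

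**Working it through.** The plan states no figure for late related SAEs, so there is none to reproduce. The check traces each kind of event through the rules and then gives the scale of one omitted patient.

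**Step 1. Where each event goes**

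| Event | Collected? | AE table (SAP 6.5.2)? | Listing (SAP 6.5.2)? |
|---|---|---|---|
| SAE with onset in the window | Yes | Yes | Yes |
| AE with onset in the window, fatal later | Yes | Yes, as a TEAE that led to death | Yes |
| Related SAE with onset after the window | Yes, should be reported (Protocol 9.3.1) | No | Yes |
| Death not due to a TEAE | Yes (survival follow-up) | No | Yes, with cause |

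The third and fourth rows are the gap. The second row limits it: TEAE status depends on onset, so a late death from an in-window event is still counted.

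**Step 2. SAP against protocol**

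On its face, Protocol 10.5.2 would have SAEs and deaths summarised without an onset limit. SAP 6.5.2 gives serious TEAEs, TEAEs that led to death, and a death listing. The SAP is narrower on that reading and matches the protocol on the synopsis reading. It also names no table of treatment-related serious TEAEs even inside the window; serious and related events are tabulated separately.

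**Step 3. Size of one omitted patient**

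Inputs: N = 13 enrolled (SAP 8) and N = 100 planned (SAP 5). Share = 1/N; intervals are two-sided 95% Clopper-Pearson.

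- N = 13: 1/13 = 7.7% (0.2% to 36.0%) becomes 0/13 = 0% (0% to 24.7%). Check on the last limit: 1 − 0.025^(1/13) = 0.247.
- N = 100: 1/100 = 1.0% (0.03% to 5.4%) becomes 0/100 = 0% (0% to 3.6%).

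**Step 4. Chance of at least one such patient**

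P = 1 − (1 − p)^N, where p is the chance that a patient has a late related SAE. The documents do not give p. The range below is assumed, and it takes patients as independent.

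| Assumed p | N = 13 | N = 100 |
|---|---|---|
| 0.5% | 6.3% | 39.4% |
| 1% | 12.2% | 63.4% |
| 2% | 23.1% | 86.7% |
| 5% | 48.7% | 99.4% |

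The rate below 1% that Protocol 1.8 quotes for myelodysplastic syndrome and leukaemia with PARP inhibitors is not a rate of post-window events, and is not used as one.

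**The case against.** A reader might infer that the omission biases the secondary safety endpoint in the drug's favour. The documents do not support that. Protocol 2.2.2 and SAP 4.2 define the endpoint as the incidence, timing and severity of TEAEs, so a post-window event is outside it by definition.

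A reader might also infer that late related toxicity is lost or has been understated. That too goes further than the text:

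- The sentence after the restriction sends every AE to the listings, and every death is listed with its cause. With 13 patients the listings can be read in full.
- Deaths also appear in the disposition table as a reason for leaving the study (Protocol 5.6.4, SAP 6.3.1), though without cause or relationship to drug.
- Understatement requires at least one such event in a patient not already counted. Nothing in the documents shows that one occurred.

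The conflict with the protocol is open to argument, because the synopsis supports the SAP's reading. There is also a sound reason not to pool. After the window only SAEs believed related are requested, the verb is should, and after study discontinuation nobody has to look for them. Mixing passively reported events with actively collected TEAEs in one rate would combine two levels of ascertainment.

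All of this stands. It argues against changing the TEAE definition and against any claim of bias. It does not argue against separate, labelled rows, and it leaves Protocol 10.5.2 and the synopsis in disagreement.

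**Conclusion.** The point holds as a minor gap in reporting. SAP 6.5.2 tabulates less than the protocol collects on related SAEs and deaths, and less than Protocol 10.5.2 appears to promise, and SAP 8 does not record the difference. If such an event occurs in a patient not already counted, the tabulated rate of related serious or fatal toxicity is too low by 7.7 percentage points per patient at N = 13, or 1.0 point at N = 100.

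This rests on two conditions: that onset, not attribution, decides TEAE status, as SAP 6.5.2 says, and that at least one such event occurs, which the documents do not tell us. The TEAE endpoint is unaffected and no event is lost from the record. At 13 patients the practical effect is likely to be small.

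**What to change.** Leave the TEAE definition and the TEAE tables unchanged. Extending the definition in the SAP alone would depart from Protocol 10.5.2, and a general extension to related AEs would pick up late non-serious events haphazardly, since only SAEs are requested after the window.

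Add to SAP 6.5.2, by cohort and overall:

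- patients with any reported SAE from first dose onward;
- patients with any treatment-related SAE, using the existing rule that missing causality counts as related;
- all deaths.

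Split each row into within and after the TEAE window. Add a footnote that post-window SAEs are limited to those believed related, were not actively sought after study discontinuation, and may have followed another therapy.

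Also reconcile the Safety Analysis paragraph of the synopsis with Protocol 10.5.2. If the narrower reading is the intended one, say so in SAP 8 with the reason.

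The cost is a short paragraph and a few rows from data already collected. The downside is that the late counts are less completely ascertained and may be confounded by later treatment, which is why they stay separate and labelled.
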